3.1 Primary outcome of the main study - Modified WHO grading

3.1.1 Definition of the primary outcome

The proportion of participants progressing from mild to severe COVID-19 pneumonia within 14 days. Where severe COVID-19 pneumonia is defined by a modified WHO COVID-19 Ordinal Score ≥ 5 (on the 9 point scale), comprising the following indicators of disease severity: Death (9) OR Requirement for invasive ventilation plus organ support (8) Requirement for invasive ventilation (7) OR Requirement for non-invasive ventilation including CPAP or high flow oxygen (6) OR O₂ saturation < 90% on \geq 60% inspired oxygen (5). These are captured in the database as follows:

Modified WHO COVID-19 Ordinal Score	Database
(9) Death	
(8) Requirement for invasive ventilation plus organ support	Has the patient required renal replacement therapy? OR Has the patient required ECMO? OR Has the patient required inotropic support? AND Has the patient required intubation and mechanical ventilation?
(7) Requirement for invasive ventilation	Has the patient required intubation and mechanical ventilation?
(6) Requirement for non-invasive ventilation including CPAP or high flow oxygen	Has the patient required NIV, CPAP or high flow nasal oxygen?
(5) O ₂ saturation < 90% on ≥60% inspired oxygen	Has the patient's oxygen saturation been < 90% on 60% inspired oxygen?

3.1.2 Statistical model at stage 1

The stage one primary analysis will consist of fitting two separate binomial regression models for the RUX vs SOC and FOS vs SOC comparisons in order that we can undertake an adjusted analysis using a propensity score approach. Specifically a generalized linear model with WHO COVID-19 status (<5 or ≥ 5) as the outcome and treatment group as a covariate. We will adjust the treatment effect for the

following prespecified covariates using a propensity score approach. The propensity score model will include:

- baseline WHO COVID-19 score (3 or 4)
- age ($<65 \text{ or } \ge 65$)
- receipt of dexamethasone (prior randomisation or up to 1 day post randomisation)
- receipt of tociluzimab (prior randomisation or up to 1 day post randomisation)

In the event that all participants are on one of the effective treatments that covariate will be removed from the propensity score. We will adjust using the propensity score from a logistic regression model including the above covariates. We will also fit an unadjusted generalized linear model with WHO COVID-19 status (<5 or ≥ 5) as the outcome and treatment group as a covariate.

The models will be fitted with a binomial distribution and logit link function and the treatment effect will be reported as an odds ratio with corresponding 95% confidence interval and p-values. P-values will be one-sided and judged at the 0.25 level. Given that the number of sites is likely to be small we will not include site as a covariate in this stage 1 analysis.

Every effort will be made to obtain follow-up data for all participants including those that stop treatment. The number and proportion of participants missing WHO COVID-19 status by treatment group and visit will be tabulated (see section 2.5 above). For participants who are discharged early the assumption will be made that they did not progress to grade 5 WHO scale. If there is a >5% rate of missing outcomes after this, we will impute missing WHO COVID-19 data in the primary analysis model using multiple imputation under the assumption of missing at random (MAR). That is the probability of being missing is not dependent on the values of unobserved data, conditional on the observed values of the variables included in the analysis model. Imputation under MAR using chained equations following the guidance of White et al. will be undertaken.⁴ Variables in the imputation model will include the variables in the primary analysis model described above plus baseline WHO COVID-19 score (3 or 4), age (<65 or ≥65), receipt of dexamethasone and/or tociluzimab at the time of or prior to randomisation into MATIS. Additional auxiliary variables that are suspected to be associated with the outcome and are predictors of missingness will also be included. These are receipt of any effective treatments post randomisation as a result of co-enrolment when occurring postrandomisation, and receipt of known effective treatments dexamethasone and tociluzimab postrandomisation (>1 day post randomisation) and WHO COVID-19 scores at day 1 and day 7. Using White et al.'s rule of thumb we will impute m datasets based on the percentage of participants with incomplete outcomes, where m will be rounded to the nearest 10, for example if 8% of participants have incomplete primary outcome then m=10 will be used.

Before undertaking the multiple imputation as described above we will impute any missing baseline data deterministically only using other baseline data, this includes the baseline WHO COVID-19 status, age, receipt of dexamethasone and/or tociluzimab at the time of or prior to randomisation into MATIS. To do this we will impute missing values with the mean values of observed data. In line with White et al., outcomes will be imputed separately for each treatment group.

Imputed datasets will then be analysed using the primary analysis model described above.

A sensitivity analysis on the primary analysis will be undertaken if greater than 5% of outcome data are missing to examine the missing at random assumption. We will examine extreme examples assuming 1) that all participants with missing outcome had poor outcome e.g. all missing >=5, and 2) that all participants with missing outcome had good outcome e.g. all missing <5.

i. Compliance

Adherence to assigned treatment (RUX and FOS) will be calculated for each participant as the proportion of dose received per day of the prescribed dose per day and presented as the percentage received. This will be summarised by treatment group as described in section 2.6 above.

To explore the impact of compliance with the planned treatment protocol, we will undertake a perprotocol analysis to examine the treatment effect in those that take most of the treatment. We will define 'per-protocol' population as individuals who receives $\geq 90\%$ of prescribed dose and refit the primary analysis model on this population.

ii. Time of enrolment

An exploratory analysis of the primary outcome will be undertaken in order to assess the impact of time of enrolment into the MATIS study. A categorical variable will be created by splitting the recruitment period into quartiles such that participants are grouped into approximately four equal sized groups based on time of enrolment into the MATIS study. A crude odds ratio will be calculated for each quartile.

All stage 1 analysis of the WHO COVID-19 grades will be completed by the independent statistician in Newcastle University to ensure the trial statistician remains blind and only DMC members will see these results.

3.1.3 Statistical model at stage 2

The stage two primary analysis will consist of fitting one binomial regression model regardless of whether one or two experimental treatments progress from stage one. Specifically a generalized linear model with WHO COVID-19 status (<5 or \ge 5) as the outcome and treatment group, baseline WHO COVID-19 score (3 or 4), age (<65 or \ge 65), receipt of known effective treatments dexamethasone and/or tociluzimab, prior vaccination against COVID-19 (y/n) and receipt of paxlovid and/or molnupiravir at the time of or prior to randomisation into MATIS as covariates will be fitted. Effective treatments will be included as separate covariates in the primary analysis model. Given the anticipated small number of sites in this study, site will also be included in the model as a fixed effect. In the event that all participants are on one of the effective treatments that covariate will be removed from the model.

If including site as a fixed effect results in unstable model estimates e.g. if there are a number of sites with very few randomisations we will exclude site from the model and we will only adjust for baseline WHO COVID score, age group, receipt of known effective treatments dexamethasone and/or tociluzimab, prior vaccination against COVID-19, and receipt of paxlovid and/or molnupiravir.⁶ We will also consider not adjusting for paxlovid and/or molnupiravir if the number of participants receiving these are low. If after removing sites and treatments the model is not stable due to event rate:covariate ratio we will adjust for all covariates using a propensity score approach.

The model will be fitted with a binomial distribution and logit link function and the treatment effect will be reported as an odds ratio with corresponding 95% confidence interval and p-values. P-values will be one-sided and judged at the 0.027 level. Therefore, a two-sided p-value < 0.054 will be used to indicate a significant treatment effect.

The stage two model to be fitted to estimate the treatment effects will be:

$$logit(\pi_{ij}) = \beta_{0} + \beta_{1}RUX_{ij} + \beta_{2}FOS_{ij} + \beta_{3}WHO_{ij}^{0} + \beta_{4}AGE_{ij}^{0} + \beta_{5}DEX_{ij}^{0} + \beta_{6}TOC_{ij}^{0} + \beta_{7}VAC_{ij}^{0} + \beta_{8}PAX_{ij}^{0} + \beta_{9}MOL_{ij}^{0} + \beta_{10}SITE_{1} + \beta_{11}SITE_{2} + \cdots + \beta_{12}SITE_{i-1}$$

 RUX_{ij} : dummy variable for treatment ($RUX_{ij} = 0$ or 1) for participant i in jth site

 FOS_{ij} : dummy variable for treatment ($FOS_{ij} = 0$ or 1) for participant i in jth site

 WHO_{ij}^0 : dummy variable for baseline WHO COVID-19 value for participant i in jth site (WHO_{ij})

0 or 1 where 0 indicates score of 3 and 1 indicates score of 4)

 AGE_{ij}^{0} : dummy variable for age-group ($AGE_{ij} = 0$ or 1 where 0 indicates <

65 years and 1 indicates \geq 65) for participant i

 DEX_{ij}^0 : dummy variable for receipt of dexamethasone at the time of or prior to randomisation (includes day of randomisation or one day post randomisation) ($DEX_{ij} = 0$ or 1) for participant i

 TOC_{ij}^0 : dummy variable for receipt of tociluzimab at the time of or prior to randomisation (includes

day of randomisation or one day post randomisation) ($TOC_{ij} = 0$ or 1) for participant i

 VAC_{ij}^0 : dummy variable for prior vaccination against COVID-19 at the time of or prior to randomisation (includes day of randomisation or one day post randomisation) ($VAC_{ij} = 0 \ or \ 1$) for participant i

 PAX_{ij}^0 : dummy variable for receipt of paxlovid at the time of or prior to randomisation (includes day of randomisation or one day post randomisation) ($PAX_{ij} = 0 \text{ or } 1$) for participant i

 MOL_{ij}^0 : dummy variable for receipt of molnupiravir at the time of or prior to randomisation (includes day of randomisation or one day post randomisation) ($MOL_{ij} = 0$ or 1) for participant i $Site_j$: dummy variable for each of the jth sites

 π_{ij} : probability of WHO COVID-19 \geq 5 for the ith participant in jth site

To account for missing outcomes in the primary analysis model we will impute missing WHO COVID-19 status using multiple imputation under the assumption of missing at random (MAR) as described in the primary statistical model at stage 1 section 3.1.2 plus the imputation model will contain the following additional variables: prior vaccination against COVID-19, and receipt of paxlovid and/or molnupiravir at the time of or prior to randomisation into MATIS, plus post-randomisation receipt of paxlovid and/or molnupiravir. Multiple imputation will be used for the final analysis regardless of levels of missingness at this stage.

As well as reporting odds ratios and 95% CIs, the model will be used to estimate the difference in proportion of participants with modified WHO COVID-19 Ordinal Score ≥ 5 .

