#### 3.2 STUDY SITES

The trial will commence at one site, Imperial College Healthcare NHS Trust in the UK, with further UK based sites that will include Reading, Hillingdon, London North West University Healthcare NHS Trust (Northwick Park Hospital and Ealing Hospital), Leeds and Sheffield Teaching Hospitals NHS Foundation Trust.

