#### 4.2 STATISTICAL ANALYSIS PLAN

Analysis will be on an intention to treat (ITT) population including all randomized patients, multiple imputation will be used to include participants who have missing outcome data. Comparisons for efficacy will be made between all participants randomised to the different treatment arms, irrespective of whether they received their allocated treatment ("ITT" analyses). Comparisons for safety will be made between all participants randomised to the different treatment arms who have received at least one dose of study medication. Multiple imputation makes a missing at random assumption and a sensitivity analysis around the assumptions made will be performed using controlled multiple imputation that permits exploration of a not missing at random assumption. A complete case analysis will also be performed. The primary outcome will be analysed as binary with participants categorised WHO COVID-19 Ordinal Score <5/  $\ge 5$  by 14 days.

For Stage 1 analysis (after a target recruitment of 171 participants) we will calculate the Wald test statistics from separate logistic regression models for RUX vs SOC and FOS vs SOC, adjusted for stratification variables, with 95% confidence intervals and p-values. P-values will be one-sided and judged at the 0.25 level.

If at least one intervention arm shows promise, then stage 2 will recruit a further 95 per arm (the maximum combined sample size of stages 1 and 2 is 456 patients). The stage 2 analysis will use a one-sided p-value

MATIS version 4.0 dated 2nd November 2022

IRAS: 282552 Page **27** of **57** 

threshold of 0.027. This has been chosen to control the maximum chance of recommending an ineffective treatment at 0.05.

Contamination is a potential threat in many C19 trials, as standard of care is continuously evolving, and coenrolment to ongoing trials present a real challenge if unequal enrolment occurs across arms. For participants who were co-enrolled to a trial at the same time, or prior to the randomisation to this trial, we will adjust the final analysis though covariate adjustment. For participants who were subsequently co-enrolled after randomisation, we treat this as a post-randomisation variable and undertake a supplementary analysis to adjust for this variable along with the receipt of post-randomisation rescue medication.

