In Stage 2 a logistic regression model will be used to assess the treatment effect of RUX and FOS compared to SOC. The model will include the treatment arms, baseline modified WHO Severity Score, trial co-enrolment at baseline, and randomisation stratification variables viz. site and age (<65 vs ≥65). As well as reporting OR and 95% CIs, the model will be used to estimate the difference in proportion of participants with modified WHO COVID-19 Ordinal Score ≥5. The treatment effect in the absence of post-randomisation co-enrolment and receipt of rescue medication will be estimated in a supplementary analysis where participants' outcomes after either will be treated as missing and a controlled multiple imputation using a delta based approach will be used.

For the primary outcome, progression to severe COVID-19 disease within 14 days, discharge alive from the admitting hospital before 14 days will assume safety from the event (in the absence of additional data confirming otherwise). An additional sensitivity analysis will be performed if there is a change of dose after review of the first thirty patients.

For time-to-event analyses required for secondary endpoints such as time to discharge, each treatment group will be compared with SOC and modelled using a proportional hazards time-to-event model adjusted for randomisation stratification variables. Kaplan-Meier estimates for the time to event will also be plotted (with confidence intervals). The log-rank 'observed minus expected' statistic (and its variance) will be used to estimate the average event rate ratio (and its confidence interval) for those allocated to each treatment group versus the no additional treatment group.

Pre-specified subgroup analysis will be conducted for the primary outcome using the statistical test for interaction (or test for trend where appropriate) for the following: disease severity as graded by the WHO

MATIS version 4.0 dated 2nd November 2022

IRAS: 282552 Page **28** of **57** 

Imperial College Healthcare

COVID-19 Ordinal Severity Scale; time since onset of symptoms; sex; age; and comorbidities obesity, chronic heart, lung, kidney and liver disease, diabetes, immunocompromised and smoking status. Pre-specified subgroup analyses will also be conducted for the primary outcome using the statistical test for interaction (or test for trend where appropriate) for patients with admission CRP >200mg/L and/or D-dimer 2500ng/mL.

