#### 6.2 RANDOMISATION

Patients will be randomized to one of three actively recruiting trial arms, RUX, FOS or SOC. Eligible patients will be allocated using a central web-based randomisation service that uses randomisation sequences with random block sizes that are stratified by age (<65 vs ≥65) and site. If stage 2 occurs with one intervention arm stopped then the randomisation ratio will be 1:1.

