1.8 Brief description of proposed analysis

Efficacy analysis population: We will use the intention-to-treat (ITT) population which includes all randomised participants analysed in the treatment arm to which they were allocated to regardless of treatment subsequently received, multiple imputation will be used to account for any missing data such that all randomised participants are included in the final analysis. At the formal interim analysis multiple imputation will be undertaken if greater than 5% of outcome data are missing, if \leq 5% missing a complete case analysis will be undertaken.

Safety analysis population: We will include participants who received at least one dose of study medication and analysis will be according to treatment received, regardless of randomised treatment assignment.

The formal interim analysis will be conducted after 171 participants have been recruited and have completed 14 days of follow-up after randomisation. If an experimental treatment is recommended to continue an additional 95 participants will be recruited for each arm that continues and final analysis will be completed after all participants have completed 28 days of follow-up after randomisation.

Formal interim and final analyses will be carried out sub-group blind and follow the ITT principle. That is, all randomised patients will be analysed in the treatment arm to which they were allocated to regardless of treatment subsequently received, multiple imputation will be used to include all randomise participants for the final analysis, at the formal interim analysis multiple imputation will be undertaken if greater than 5% of outcome data are missing. The analysis of the serious adverse events will be undertaken on the safety population.

All regression analysis will include adjustment for age group (<65 years or ≥65 years) and site where appropriate, since these were stratification factors in the randomisation.

All confidence intervals will be presented at the 95% level.

For the formal interim analysis (stage 1) one-sided p-values \leq 0.25 will indicate that an experimental treatment should be recommended to continue to stage 2 and for the final (stage 2) analysis one-sided p-value \leq 0.027 will be interpreted as statistically significant for the primary outcome.

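### The SAP's stage 1 model omits site, a stratification factor the protocol says to adjust for, on the premise (few sites) that the SAP gives elsewhere when it includes site

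*SAP*

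**What the plan says.** Randomisation is by a central service that "uses randomisation sequences with random block sizes that are stratified by age"; the sentence goes on to name site (Protocol 6.2, repeated in SAP 1.6).

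For stage 1, Protocol 4.2 states: "we will calculate the Wald test statistics from separate logistic regression models for RUX vs SOC and FOS vs SOC, adjusted for stratification variables". It adds no qualifier. The same section, describing the stage 2 model, spells out the factors: "and randomisation stratification variables viz. site and age".

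SAP 1.8 sets a general rule that all regression analyses adjust for age group "and site where appropriate, since these were stratification factors in the randomisation".

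SAP 3.1.2 (stage 1) builds a propensity score from baseline WHO score, age, dexamethasone and tocilizumab, and then says: "Given that the number of sites is likely to be small we will not include site as a covariate in this stage 1 analysis".

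SAP 3.1.3 (stage 2) says: "Given the anticipated small number of sites in this study, site will also be included in the model as a fixed effect". It allows site to be removed later, in a passage that begins "If including site as a fixed effect results in unstable model estimates" and gives several sites with very few randomisations as the example. SAP 3.2.2 (ordinal model) also includes site as a fixed effect because few sites are expected.

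**The concern.** There are two problems. First, the protocol and the SAP define different models for the test that guides whether an arm continues. One adjusts for both stratification factors and the other for age only.

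Second, the reason given for the omission does not support it. A small number of sites means few extra terms, which makes site easier to include. A sound reason would be sparse sites, meaning sites with very few patients. The SAP gives that reason only as the stage 2 fallback.

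Blocked randomisation within site balances the arms on site. If site is prognostic, that balance reduces the true sampling variation of the treatment estimate, but a model without site does not credit the reduction. Its Wald statistic then varies less than a standard normal under the null, and the test runs below its nominal 25% level. At stake is a mild loss of calibration and the possibility of two different formal interim results from one trial, depending on which document is followed.

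**Working it through.** **1. The plan's own figure.** Inputs from SAP 1.5 and 1.5.1: 57 per arm, 5% missing (about 54 evaluable), control 50%, effective arm 30%, one-sided 0.25 (z = 0.6745).

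- Log odds ratio: ln(0.5/0.5) − ln(0.3/0.7) = 0.847.
- Standard error: √[1/(54×0.25) + 1/(54×0.21)] = √(0.0741 + 0.0882) = 0.403.
- Chance of passing: Φ(0.847/0.403 − 0.6745) = Φ(1.43) = 92.3%.

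The stated 92% reproduces. A pooled two-proportion test gives 93.0% and an unpooled test 93.2%. Two-stage power at 144 evaluable per arm and information fraction 171/456 = 0.375 is 89.9% (stated 90%). With one-sided 0.027 for two comparisons sharing a control (correlation 0.5), the family-wise error rate is 4.9% (stated maximum 5%). None of these calculations uses site.

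**2. Simulation A: age only against age plus site.** 171 patients, blocks of 3 or 6 within site and age group, 4,000 trials per setting. The documents do not give these assumptions: three or six equal sites, between-site SD on the logit scale of 0, 0.5 or 1.0, age log odds ratio 0.8, within-site treatment odds ratio 0.43.

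| Sites, SD | Ineffective arm passes: without → with site | Effective arm passes: without → with site |
|---|---|---|
| 3, 0.5 | 24.3 → 25.2% | 92.4 → 92.7% |
| 6, 0.5 | 24.3 → 25.6% | 91.7 → 92.6% |
| 3, 1.0 | 22.7 → 25.3% | 89.1 → 90.9% |
| 6, 1.0 | 22.7 → 25.0% | 87.9 → 89.9% |

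At SD 0 the models differ by 0.4 points or less. Monte Carlo error is about 0.7 points (ineffective) and 0.4 to 0.5 points (effective), with both models fitted to the same data. The within-site odds ratio is held fixed, so the marginal effect shrinks as site variation grows. The effective-arm levels are therefore not comparable with the stated 92%.

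**3. Simulation B: the SAP's propensity score as a covariate, without and with site.** 20,000 trials per setting, marginal 50% against 30%, 5% of outcomes missing. Assumed: WHO grade 4 in 70%, age 65 or over in 45%, dexamethasone 80%, tocilizumab 20% (both drugs non-prognostic). Log odds ratios for WHO score and age were 1.2 and 0.8 (stronger) or 0.8 and 0.5 (weaker), with site effects within ±0.8 or ±0.4. The first three rows use four sites (40/30/20/10%). The last uses six (50/20/12/10/5/3%) with the stronger effects. Sites under 10 were pooled in this simulation.

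| Setting | Ineffective arm passes: without → with site | Effective arm passes: without → with site | Effective arm at matched size: without → with site |
|---|---|---|---|
| Stronger | 24.3 → 25.1% | 94.1 → 94.5% | 94.3 → 94.5% |
| Weaker | 25.0 → 25.5% | 93.3 → 93.3% | 93.3 → 93.2% |
| None prognostic | 25.7 → 25.9% | 92.6 → 92.7% | 92.3 → 92.3% |
| Six uneven sites | 24.0 → 24.5% | 93.8 → 93.9% | 94.1 → 94.1% |

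Matched size means that each model is cut at its own null 25% point. The null SD of the Wald statistic moved from 0.938 to 0.969 in the stronger setting and from 0.957 to 0.983 with six sites. The two models fell on opposite sides of 0.25 in 1.4 to 3.0% of trials under the null and 0.6 to 1.2% under the effect.

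**4. A further run**, also under assumed site effects, gave null pass rates of 22.6 to 23.6% without site and 23.8 to 24.2% with it. The null SD rose from 0.91–0.95 to about 0.98.

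**5. Model size.** Events per comparison: 54×0.5 + 54×0.3 = 43.2. Treatment, score and three site terms (four sites) give 43.2/5 = 8.6 events per term. Six sites, as in Protocol 3.2, give 43.2/7 = 6.2. The protocol synopsis names five sites, giving 43.2/6 = 7.2.

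**The case against.** The strongest defence is that the SAP made an open, pre-specified choice. Its general rule has site included only where appropriate, and Protocol 4.2 leaves further detail to the SAP. This softens the mismatch. It does not remove it, because the protocol's stage 1 sentence carries no such latitude and the SAP's own rule gives stratification as the reason to adjust.

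The stage 2 sentence may also justify only the form (a fixed effect) and not the decision to include site. That reading is fair, so a charge of flat self-contradiction would go too far. Even so, few sites remain no reason for leaving site out.

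Sparse data is a legitimate worry. The trial opens at one site (Protocol 3.2), which may dominate at the interim, and the SAP's stage 2 fallback removes site first and turns to a propensity score later. But SAP 3.1.2 does not give sparseness as its reason, and the existing fallback already deals with it.

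Site could instead go inside the propensity score with no extra outcome-model terms. In the further run this left the null SD at 0.91 to 0.95, so calibration was not restored. Stratified blocks already balance site, so site adds little to a score that predicts treatment.

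Finally, the consequence is limited, and this stands. The stage 1 rule is non-binding (SAP 1.5.1), the p-value is read on a continuous scale (Protocol 4.1), and site is in the planned stage 2 model.

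**Conclusion.** The mismatch is real and minor. The textual part is certain. The SAP names protocol version 2.2 as its basis and the protocol supplied is 4.0, but the amendment log records no change to the stage 1 model that would explain the difference.

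The numerical part rests on assumed site effects. Where these are moderate or larger, the test without site passes an ineffective arm about 22.5 to 24.5% of the time, against about 24 to 25.5% with site. Where they are weak or absent, both models sit near 25%. The models disagree at the threshold in about 1 to 3% of simulated trials.

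A reader might infer that the interim is invalid, that error is inflated, or that an effective arm is materially more likely to be dropped. The documents do not support this. Omission makes the test conservative. The 5% family-wise error rate is calculated as if the stage 1 rule were not followed. The 92% and 90% reproduce from calculations that do not involve site. The gaps of up to 2 points for the effective arm in simulation A arise at large assumed site variation with a fixed cut-off. In simulation B, matching size leaves differences of 0.2 points or less. Nor is the propensity score for the other covariates in question.

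**What to change.** In SAP 3.1.2, replace the sentence excluding site with: *Each adjusted stage 1 model will include site as a fixed effect, alongside the propensity score; if this gives unstable estimates, for example because some sites have very few randomisations, site will be excluded, as in section 3.1.3.*

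If site is still to be omitted, or if stage 1 has already been run (the documents do not say), record the departure from Protocol 4.2 with a valid reason, which would be sparse sites and not few sites. Report the site-adjusted model as a sensitivity analysis.

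The cost is one sentence; site is already known at randomisation. The model gains a few terms, at about 6 to 9 events per term. The ineffective-arm pass rate rises slightly but stays close to the nominal 25%. If more than 5% of outcomes are missing, site would also enter the stage 1 imputation model as an analysis variable. That imputation is done separately by arm, so small sites could be sparse there and the same fallback should apply.

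### The SAP's missing-outcome check gives every arm the same outcome and covers stage 1 only; the final analysis lacks the controlled imputation and complete-case analysis that the protocol requires

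*SAP*

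**What the plan says.** **Protocol 4.2** makes multiple imputation under missing at random (MAR) the primary handling of missing outcomes. It then requires a sensitivity analysis by "controlled multiple imputation that permits exploration of a not missing at random assumption", and adds: "A complete case analysis will also be performed".

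**SAP 3.1.2 (stage 1)** says: "A sensitivity analysis on the primary analysis will be undertaken if greater than 5% of outcome data are missing". It names two scenarios. One assumes "that all participants with missing outcome had poor outcome e.g. all missing >=5". The other makes the opposite assumption and counts every missing outcome as below 5. Neither distinguishes between arms.

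**SAP 3.1.3 (stage 2)** says: "Multiple imputation will be used for the final analysis regardless of levels of missingness at this stage". The imputation is under MAR, "as described in the primary statistical model at stage 1 section 3.1.2", with some added variables. The section names no not-missing-at-random analysis and no complete-case analysis of the primary outcome. Neither does SAP 3.1.5, whose exploratory analyses cover co-enrolment, mediation, compliance and time of enrolment. The sensitivity analysis mentioned in SAP 3.1.4 concerns model misspecification.

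**The concern.** A treatment comparison is most exposed to missing data when the unobserved participants fare differently in the two arms. The trial is open label, so reasons for leaving follow-up could differ by arm, although the documents give no evidence that they do. Neither SAP scenario represents that case. When similar numbers are missing in each arm, the two scenarios agree almost by construction, and their agreement says little about robustness.

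The second part concerns where the check sits. The stage 1 result is a non-binding guide to stopping for futility. The stage 2 result decides whether a drug is recommended, and there the SAP specifies no check of MAR at all, although the protocol requires one. A final result that depends on what happened to a handful of missing participants could then be reported without that being visible.

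**Working it through.** **1. The plan's own figures.** SAP 1.5 gives 57 per arm at stage 1 and 152 per arm in total, 50% versus 30%, one-sided 0.25 then 0.027, 5% missing outcomes and 90% power. I took power as P(Z1 > z(0.75) and Z2 > z(0.973)), bivariate normal with correlation √(n1/n2). After 5% loss (54.15 and 144.4 per arm) this gives 0.895 with the pooled variance and 0.900 with the unpooled. With no loss it gives 0.908 and 0.912. The stated 90% reproduces. So does the inflation: 144/0.95 = 151.6, rounded up to 152.

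**2. Why equal missing counts make the check uninformative.** Let N be the number randomised per arm, e1 and e0 the observed events on drug and SOC, and m1 and m0 the numbers missing.

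- All poor: risk difference = (e1 + m1 − e0 − m0)/N
- All good: risk difference = (e1 − e0)/N
- Poor on drug, good on SOC: risk difference = (e1 + m1 − e0)/N

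All poor and all good differ by (m1 − m0)/N, which is zero when m1 = m0. The opposed case differs from all good by m1/N whether or not the counts are equal.

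**3. Numbers.** The test is the unadjusted one-sided Wald test on the log odds ratio, z = [ln(a/b) − ln(c/d)] / √(1/a + 1/b + 1/c + 1/d), where a and b are events and non-events on drug, and c and d the same on SOC. All counts are assumed for illustration; they are not trial data.

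Worked example, case B below:

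- Complete cases, 54/144 versus 72/144: z = [ln(54/90) − ln(72/72)] / √(1/54 + 1/90 + 1/72 + 1/72) = −0.511/0.240 = −2.13, p = 0.0165.
- Poor on drug, good on SOC, 62/152 versus 72/152: z = [ln(62/90) − ln(72/80)] / √(1/62 + 1/90 + 1/72 + 1/80) = −0.267/0.232 = −1.15, p = 0.124.

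| Case (152 per arm) | Observed, drug vs SOC | Complete case p | All poor p | All good p | Poor on drug, good on SOC p |
|---|---|---|---|---|---|
| A: design effect, 8 missing per arm (8/152, about 5%) | 43/144 vs 72/144 | 0.0003 | 0.0004 | 0.0003 | 0.007 |
| B: smaller effect, 8 missing per arm | 54/144 vs 72/144 | 0.0165 | 0.0195 | 0.0183 | **0.124** |
| C: design effect, 15 missing per arm (about 10%) | 41/137 vs 68/137 | 0.0005 | 0.0010 | 0.0007 | **0.081** |
| D: unequal counts, 14 missing on drug and 2 on SOC | 50/138 vs 75/150 | 0.0095 | **0.068** | 0.002 | **0.103** |

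Bold marks values above 0.027. In case B both SAP scenarios give a risk difference of (54 − 72)/152 = −0.118, and the opposed case gives (62 − 72)/152 = −0.066. The opposite extreme, good on drug and poor on SOC, gives p = 0.0014.

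**4. Stage 1.** With 57 per arm, an assumed 3 missing per arm and 22/54 versus 27/54 observed, all poor gives p = 0.175 and all good 0.172. The opposed case gives 0.353, on the other side of the 0.25 guide.

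**The case against.** The strongest points on the other side are these.

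- **The check is not blind to all differential missingness.** A reader might infer that it is. Case D shows otherwise: with 14 versus 2 missing, all poor moves p from 0.0095 to 0.068. This stands. The gap concerns differing outcomes among the missing, not differing numbers missing.
- **The protocol's requirement has not been withdrawn.** Protocol version 4.0 still carries it, and the SAP refers to the protocol (version 2.2) for full design details. SAP 3.2.3 rules out sensitivity analysis for the component outcomes, which hints that one was intended for the primary outcome. So this is a failure to align two documents, not a stated decision to remove a safeguard. But Protocol 4.2 leaves the details to the SAP, and the SAP gives none for stage 2. Its reference from 3.1.3 back to 3.1.2 is attached to the MAR imputation, not to the sensitivity scenarios.
- **The protocol does not promise delta-based imputation for missing outcomes.** Protocol 4.2 says controlled there. Its delta-based wording belongs to a separate supplementary analysis of post-randomisation co-enrolment and rescue medication. Arm-specific deltas are therefore a recommendation of this review.
- **The exposure may be small.** Early discharge counts as no event, follow-up is also sought through notes and registries, and outcomes are imputed separately by arm with day 1 and day 7 scores as auxiliary variables. In case A even the opposed extreme passes. Arm-opposed extremes are bounds, not plausible estimates. All of this stands and limits the size of the point, but it does not supply the missing analysis.

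**Conclusion.** The point holds in this form. The SAP's only check of MAR gives every arm the same outcome, so it cannot show whether a result depends on missing participants faring differently by arm. It is specified only for the interim look. The final primary analysis lacks both the controlled imputation and the complete-case analysis of Protocol 4.2, and the SAP gives no reason.

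The size depends on assumed counts and an unadjusted test. At about 5% missing and the full design effect, the result survives the opposed extreme. With a smaller effect (54/144 versus 72/144), or with about 10% missing at the design effect, it does not, while both SAP scenarios still pass 0.027. The documents do not support the stronger inference that a positive result would be fragile in general. The primary estimate itself is unaffected. The change is worth making because it is cheap and gives the confirmatory analysis a check that can detect this dependence.

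**What to change.** 1. In SAP 3.1.3, specify for the final primary analysis the complete-case analysis and a controlled multiple imputation with a separate delta for each arm, reported as a tipping point: the departures from MAR at which the one-sided p-value crosses 0.027. If either analysis is to be left out, give the reason for departing from Protocol 4.2.
2. Add the two arm-opposed extremes (poor on drug and good on SOC, and the reverse) to the two scenarios in SAP 3.1.2, and apply all four in SAP 3.1.3. Keep the existing two, because they detect unequal missing counts.

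The cost is SAP wording and a few extra runs, with no new data collection. The downside is a sensitivity table that may look less favourable. The tipping-point results should sit beside the extremes so that readers can judge how plausible the extremes are.
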